mls	Millilitres, volume of antibiotic or placebo to be taken by the child
ISF	Investigator Site File
NRES	National Research Ethics Service
PC-CTU	Primary Care – Clinical Trials Unit
PE	Pulmonary Embolism
PI	Principal Investigator
PSC	Programme Steering Committee
PSS	Personal Social Service

QALY	Quality-Adjusted Life-Years
QoL	Quality of Life
QP	Qualified Person
R&D	NHS Trust R&D Department
RCT	Randomised Controlled Trial
REC	Research Ethics Committee
SAE	Serious Adverse Event
SAR	Serious Adverse Reaction
SMPC	Summary of Medicinal Product Characteristics
SOP	Standard Operating Procedure
SUSAR	Suspected Unexpected Serious Adverse Reactions
TSC	Trial Steering Committee
VAS	Visual Analogue Scale

1. OVERVIEW OF RESEARCH

Design: Pilot RCT

Target population: Adults with uncomplicated acute rhinosinusitis: acute sinus discomfort (<=4 weeks), and 2 of reported nasal obstruction, reported purulent discharge, or pus visible).

Trial groups: a) Immediate antibiotics (this approximates usual care: currently nearly 95% of patients receive antibiotics) b) advice to use high volume hypertonic saline nasal irrigation with a delayed prescription for antibiotics.

Baseline measures: Structured history/examination. Nasal swabs for bacteriology (optional to maximise participation).

Feasibility outcomes: follow-up rates, recruitment rates, adherence/acceptability of the intervention. **Primary outcome**: Antibiotic use.

Other outcomes: duration of moderately bad symptoms (using a validated symptom diary; variables (using 7 point Likert scales): nasal blockage, discharge, unpleasant taste/smell, facial pain, pain on bending, impaired activities, generally unwell, sleep disturbance.

Secondary outcomes: symptom duration until little/no problem; mean symptom score; development of new/worsening symptoms. Health related quality of life (EQ5D). Reconsultations/resource use during the next month.

Sample size: Feasibility estimates: to estimate follow-up rates in each group between 65% and 80% assuming we want to be reasonably sure that the follow-up rate is not 50% in each group (i.e.95% confidence intervals of +/- 15%) then 41 per group are needed. We also anticipate that it should be possible for the intervention group to achieve use of antibiotics of around 65% or less. To estimate this proportion with 95% confidence intervals of +/- 15% (i.e. that antibiotic use is 80% or less) 41 per group is also needed. To allow for loss to follow-up more than 100 patients are needed.

Feasibility. Our previous JAMA trial recruited 238 individuals/4 years with one RA (one centre), but recruitment is currently more challenging. We therefore estimate that with one RA at the coordinating centre and P/T RAs in two other centres will allow us to recruit our target efficiently in 2 winter seasons

2. LAY SUMMARY

Acute sinus infections are one of the commonest infections managed in primary care, Currently GPs prescribe antibiotics to most patients presenting with sinusitis, the highest of any of the common acute infections presenting in adults, at over 90%. The trouble with prescribing for most people is that we are using antibiotics too much which is causing the bacteria to become resistant, which is likely to lead in the future to serious infections becoming untreatable from 'superbugs'. Alternatives to the initial management with antibiotics are needed.

Previous studies have tried nasal irrigation using salt solution for colds but the studies are small and not conclusive. There have also been studies of nasal irrigation in chronic sinus infections which do show some benefit. A large study in chronic or recurrent sinusitis in primary care showed that most people can learn to do nasal irrigation with simple advice and a short video to show how it is done, find it acceptable and will keep doing it over several weeks. However, there was some evidence that the approach to help people use nasal irrigation could be made more effective, dealing with key barriers or difficulties more effectively. There have been no good studies of saline irrigation in acute sinusitis.

In a separate study, we have worked together with patients to optimise how we help patients use sinus irrigation, making sure that we are providing all the necessary advice and materials to help deal with any issues or problems patients might have. The study will randomise more than 100 people with acute sinus infections presenting in primary care to either a) immediate antibiotics (current usual treatment in primary care) or b) advice to do nasal irrigation for up to 3 weeks with a 'back-up' or delayed antibiotic prescription (a prescription that can be used if the sinusitis does not settle). Participants will fill out a daily symptom diary which will allow us to see whether irrigation makes any difference to symptom severity, or to the duration of illness, and whether antibiotic were used.

Participants who are happy to have further tests will have a swab of the nose.

This study will provide evidence of recruitment and follow-up rates, and is also likely to provide preliminary evidence about whether antibiotic use is likely to be reduced, in order to provide sufficient evidence for a larger application for a full trial.

3. BACKGROUND AND RATIONALE

Acute sinusitis like complaints are a common presentation in primary care with GPs seeing 50 or more cases per year on average (1) and cause significant morbidity, anxiety, lost time from work and school, antibiotic consumption, and treatment costs (2). The costs of antibiotic prescribing for the condition has been estimated at approximately 10 million pounds per year in the UK, and 2.4 billion dollars per year in the USA(3). Increasing antibiotic resistance in the community is a matter of ongoing international concern, in considerable part driven by antibiotic prescribing in primary care (4, 5). In contrast to the limited benefit from antibiotics, antibiotic prescribing rates remain very high, especially for sinusitis where by far the highest percentage of patients receive antibiotics when compared with any other acute respiratory infection (6) - 91% of patients in the UK. The problem with limiting antibiotic prescribing in acute sinusitis is that the natural history is prolonged. A systematic review estimated a median duration of nearly 3 weeks (7) and a primary care trial in the UK for individuals more likely to have bacterial infections the illness lasted a median of 2 weeks (8). Faced with such an unpleasant condition where the GP has little else to offer it is not surprising that prescriptions for antibiotics remain the highest among all RTIs. Alternatives to the initial prescribing of antibiotics are sorely needed.

A Cochrane review of nasal irrigation for chronic or recurrent sinusitis (9) concluded that nasal irrigation was helpful. However most of the trials were small, mainly from secondary care settings, had high heterogeneity, and the review documented symptom data from only 129 participants. A more recent review with more selective inclusion criteria (2 studies)(10) concluded that there was some evidence of benefit with high volume nasal irrigation but that the quality of evidence was limited.

We are aware of two trials that have included some participants from primary care: Rabago et al(11) (n=76) assessed a gravity based high volume nasal irrigation device compared to routine care among mainly primary care participants, and Pynnonen et al.(12) (n=121) assessed a positive pressure squeeze bottle compared to saline nasal spray among volunteers from a variety of sources. Both the latter trials demonstrated effectiveness of irrigation, but included significant individual coaching in how to do nasal irrigation. More recently a large more pragmatic trial of a brief intervention to advise high volume nasal irrigation in recurrent or chronic sinusitis advised participants to use a Netipot, and provided simple instructions on a YouTube video. The trial documented some symptomatic benefit(13), but less than the previous more intensive studies. The pragmatic trial intervention was very simple, most participants even with recurrent/chronic sinusitis engaged well – most were still using nasal irrigation 6 months later, participants had fewer headaches, and they were less likely to use over the counter medication, or to report intending to see the doctor in the next attack. Nevertheless qualitative work with participants clarified that better information about overcoming initial problems could potentially have helped increase engagement in using nasal irrigation.

The literature on the use of saline irrigation for chronic or recurrent sinusitis is supported by some evidence for acute illness. A Cochrane review of trials in acute a upper respiratory illness(14) identified five RCTs (544 children (three studies); 205 adults (two studies)) which compared saline irrigation to routine care or other nose sprays. The authors concluded that nasal saline irrigation possibly has benefits for relieving the symptoms of acute URTIs, but that the trials were generally too small and had a high risk of bias, advocating larger numbers and clinically meaningful outcome measures.

Considering both the evidence from chronic/recurrent disease and acute RTIs, on balance it is plausible that a relatively simple intervention, high volume saline nasal irrigation, could help both symptoms and help reduce antibiotic use.

4. AIMS AND OBJECTIVES

Hypotheses

Our hypotheses for a full trial are that saline nasal irrigation for acute sinusitis will improve symptom management and reduce antibiotic use, and that for the feasibility trial nasal irrigation will reduce antibiotic use.

Aim of the feasibility trial: To estimate use of the intervention; acceptability of randomisation; rates of follow-up, recruitment and antibiotic use, in order to provide sufficient evidence for a full trial application

Objectives:

• To conduct a pilot trial of nasal irrigation for acute sinusitis

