5.1. Health Technologies being assessed

Sinus nasal irrigation

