5.7. Intervention

1) Control group: immediate antibiotic prescription. We wish to provide some estimate of the reduction in antibiotic possible compared with current practice. Since more than 90% of patients currently receive antibiotic for acute sinusitis the nearest approximation to usual care is a prescription for immediate antibiotics, combined with advice about the use of analgesics. Although the particular antibiotics used is not the focus of this investigation, in line with PHE guidance for primary care we will advise the use of Penicillin V 500mgs QDS (or alternatively Amoxicillin 500mg tds) for 1 week or Clarithromycin 500mg BD also for 1 week if participants are allergic to penicillin.

2) Advice to use nasal irrigation. In addition to the advice in the usual care arm to use simple analgesics participants will be given both written and verbal instructions and given a link to a video clip (uploaded on YouTube: http://www.youtube.com/watch?v=zgvoxkGYSU4) demonstrating how to perform irrigation. They will be asked to irrigate the nose (150 ml through each nostril) daily for up to 21 days or until symptoms settle, and a SinuCleanse 19 nasal cup ('Netipot') will be provided to each subject. Patients will make their own buffered saline irrigation solution every 1 to 2 days comprising: 1 heaped teaspoon salt, one half teaspoon baking soda and 1 pint (568 ml) tap water; how to do this will also demonstrated on the video clip. We chose this particular intervention based on the provisional evidence from a previous randomised controlled trial in primary care in chronic/recurrent sinusitis (11) and from our most recent large trial also in chronic or recurrent sinusitis (13), where most patients found it acceptable and the majority continued using nasal irrigation. Participants in this group will be offered a delayed antibiotic prescription as in our previous trials(19), and advised only to use it if symptoms are getting significantly worse or not even starting to settle a little after a further week.

All study participants in both groups will have access to usual care; further medication or referral will be at the discretion of the doctor according to the normal practice of that doctor.

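### The feasibility hypothesis credits irrigation alone, but the arms differ in irrigation and in prescribing strategy, so the contrast can only speak for the package

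*Protocol*

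**What the plan says.** **The claim.** Section 4 gives the trial's own hypothesis as "for the feasibility trial nasal irrigation will reduce antibiotic use". Section 5.1 lists a single technology under assessment, "Sinus nasal irrigation". The lay summary says the symptom diary will show whether irrigation affects severity and length of illness. Section 5.12 expects the intervention to help people leave an immediate prescription unused and, above all, to lower redemption of delayed ones.

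**The arms.** The overview describes the intervention group as receiving "advice to use high volume hypertonic saline nasal irrigation with a delayed prescription for antibiotics". Section 5.7 gives the other arm as "Control group: immediate antibiotic prescription", because "the nearest approximation to usual care is a prescription for immediate antibiotics". Intervention participants are offered a delayed prescription and are "advised only to use it if symptoms are getting significantly worse or not even starting to settle a little after a further week".

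**The outcome and analysis.** The overview names antibiotic use as the primary outcome, and section 5.12 takes it from the four-week diary. Section 5.15 plans for 90% use in the control group against 65% in the intervention group. Section 9.1 compares the randomised groups by logistic regression in an exploratory intention-to-treat analysis.

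**The concern.** The arms differ in two ways at once: irrigation advice (yes or no) and prescribing strategy (delayed or immediate). The hypothesis names only the first. The second is not a neutral background feature. Advice to hold back the prescription unless symptoms worsen or fail to settle bears on antibiotic use whether or not the participant irrigates.

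A lower rate of use in the intervention arm could therefore come from the irrigation, the delayed prescription, or both, and the trial could not tell these apart. The expectation in section 5.12 about redemption of delayed prescriptions cannot be tested either, because the control arm is not offered them. The same holds for symptoms: the comparison group has immediate antibiotics, so a difference in severity or duration would not isolate irrigation.

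What is at stake is the conclusion. Section 4 says the pilot is to supply evidence for a full-trial application, and its full-trial hypothesis is also worded around irrigation alone. A positive result reported in the hypothesis's own terms would carry an attribution that the design cannot give.

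**Working it through.** **Step 1: reproduce the plan's figure.** Inputs from section 5.15: p1 = 0.90, p2 = 0.65, alpha 0.05, power 80%, loss 20%. Sidedness is not stated; two-sided is assumed, and it reproduces the figure.

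n = [z(0.975)·√(2p̄(1−p̄)) + z(0.80)·√(p1(1−p1) + p2(1−p2))]² / (p1−p2)², with p̄ = (0.90 + 0.65)/2 = 0.775.

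- √(2 × 0.775 × 0.225) = 0.5906; times 1.960 = 1.1575
- √(0.0900 + 0.2275) = 0.5635; times 0.842 = 0.474
- n = (1.1575 + 0.474)² / 0.0625 = 42.6, so 43 per group
- Loss: 43/0.80 = 53.75, so 54 per group and 108 in total
- Power at 43 per group: z = (0.25·√43 − 1.1575)/0.5635 = 0.855, which gives 80.4%

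Both stated figures reproduce.

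**Step 2: what that contrast contains.**

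| | Immediate prescription | Delayed prescription |
|---|---|---|
| Irrigation advice | no arm | intervention arm |
| No irrigation advice | control arm | no arm |

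Only one diagonal is filled. An effect of irrigation needs two cells in the same column, and neither column has two. A regression on randomised group estimates the sum of the two changes. Baseline covariates cannot split it, because within any covariate level the two components still coincide. The estimates that section 9.4 allows for people who irrigate on more than half the days of the first week also come wholly from the delayed-prescription arm.

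**Step 3: how far attribution could be out.** The protocol gives no rate of use for a delayed prescription without irrigation, so the share s of the 25 points due to the delayed prescription is an assumption, shown over its range. The hypothetical delayed-only rate is 0.90 − 0.25s. Irrigation's own effect is the gap from there to 0.65.

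| s | Delayed-only use | Irrigation's own effect | n per arm for 80% power | Power at 43 per arm |
|---|---|---|---|---|
| 0% | 90% | 25 points | 43 | 80% |
| 25% | 83.75% | 18.75 points | 84 | 51% |
| 50% | 77.5% | 12.5 points | 205 | 25% |
| 75% | 71.25% | 6.25 points | 872 | 9% |
| 100% | 65% | 0 | none | no effect to detect |

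Every row produces the same planned data, 90% against 65%, and the same 80.4% power for the planned comparison. In the last row irrigation does nothing, and the trial would still reach significance about four times in five.

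**The case against.** The strongest reply is that this is a feasibility pilot that hides nothing. The overview, the lay summary and section 5.7 all describe the intervention group as irrigation with a delayed prescription. Testing a package against an approximation to usual care is a legitimate pragmatic choice. Section 4's aim is to estimate uptake, acceptability of randomisation, follow-up, recruitment and antibiotic use, and none of these depends on separating the components. Section 5.15 calls the between-group difference very provisional and section 9.1 calls it exploratory. On antibiotics, the lay summary speaks only of whether use is likely to fall, without crediting irrigation. All of this stands and limits how serious the point is. It does not change what the contrast measures: an exploratory label lowers the certainty claimed but does not make a package effect an irrigation effect.

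It is also fair that section 5.7 says the delayed prescription is offered, and that section 5.12 allows for some participants holding an immediate one. Departures of that kind would not be randomised, so they do not undo the confounding.

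Two stronger readings are not supported:

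- A reader might infer that the control arm overstates the reduction against usual care by 9 points, from 100% prescribed in the trial against "91% of patients in the UK" in section 3. That compares prescribing, while the outcome is reported use, for which section 5.15 assumes at least 90% in the control group. The overview's other figure for current practice, nearly 95%, would give about 5 points by the same method. Section 5.7 claims only the nearest approximation to usual care.
- A reader might infer that the pilot difference will set the main trial's effect size. The protocol does not say so. It speaks only in general terms of evidence for an application.

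**Conclusion.** The hypothesis and the contrast do not match. The trial can estimate, provisionally, the effect of irrigation advice plus a delayed prescription against an immediate prescription. It cannot show that irrigation reduces antibiotic use, and no analysis in sections 9.1 or 9.4 can recover that.

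That conclusion follows from the arms alone and needs no numerical assumption. The size does: how much of the planned 25 points belongs to irrigation is unknown, and the table in the working only shows what an assumed split would imply. The 90% and 65% are planning values, not results.

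A reader might go further and infer that the design or sample size is faulty. The documents do not support that. The numbers reproduce, the package comparison is valid, and the feasibility outcomes are untouched. The point should be fixed, but it is a correction to the claim and not a reason to hold the trial.

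**What to change.** Reword so that the claim names what is compared:

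- **Section 4:** state the feasibility hypothesis as *irrigation advice plus a delayed prescription, compared with an immediate prescription, reduces antibiotic use*.
- **Section 5.1:** name the package as the technology assessed.
- **Section 5.12:** state the expectation about prescription use as one for the package against an immediate prescription, and do not imply that the trial tests whether irrigation lowers redemption of delayed prescriptions.
- **Lay summary:** reword the sentence on symptom severity and duration in the same way.
- **Add one statement**, in section 4 or 9.1: the between-group difference will not be attributed to irrigation alone, nor used as an irrigation-only effect size for the main trial.

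The cost is wording and a narrower claim. Arms, clinical management, data collection, analysis and the 108 participants are unchanged.

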5. RESEARCH PLAN

Design: Parallel group randomised controlled pilot trial

5.1. Health Technologies being assessed

Sinus nasal irrigation

5.2. Target Population

Patients attending primary care with acute sinusitis

5.3. Recruitment

Recruitment will take place in Primary care, since this is where the vast majority of those presenting with sinusitis are managed. Eligible patients will be informed about the study by the consulting clinician or other staff at the General Medical Practice, who will explain the study and provide the patient with a patient information leaflet.

5.4. Inclusion criteria

Inclusion criteria

We will pragmatically define acute sinusitis as having sinus discomfort, and at least 2 other symptoms (2 of: patient reported nasal obstruction, patient reported purulent nasal discharge, or pus seen in the nasal cavity on inspection by the clinician). We do not propose using prior duration (e.g. the requirement for at least 7 days without improvement in the Canadian guidelines) since there is no good evidence for a particular cut-off, and our aim is to help people who are currently being treatment with antibiotics for sinusitis, many of whom present with 7 days.

5.5. Exclusion criteria

Inability to complete outcomes (reduced capacity: dementia, severe uncontrolled mental illness; terminal illness etc); head/neck cancer; HIV; immune-suppressive treatment; cystic fibrosis; pregnancy/breast feeding; other nasal disorders e.g. polyps; poor gag/swallow reflexes.

5.6. Consent

The patient will be asked to consent to the study after they have considered a patient information leaflet about the study (approved by an NHS Multi-Centre ethics committee) and had sufficient time to consider participation and ask questions. If necessary, clinicians will see other patients in order to allow sufficient time for patients to read materials and formulate questions.

5.7. Intervention

1) Control group: immediate antibiotic prescription. We wish to provide some estimate of the reduction in antibiotic possible compared with current practice. Since more than 90% of patients currently receive antibiotic for acute sinusitis the nearest approximation to usual care is a prescription for immediate antibiotics, combined with advice about the use of analgesics. Although the particular antibiotics used is not the focus of this investigation, in line with PHE guidance for primary care we will advise the use of Penicillin V 500mgs QDS (or alternatively Amoxicillin 500mg tds) for 1 week or Clarithromycin 500mg BD also for 1 week if participants are allergic to penicillin.

2) Advice to use nasal irrigation. In addition to the advice in the usual care arm to use simple analgesics participants will be given both written and verbal instructions and given a link to a video clip (uploaded on YouTube: http://www.youtube.com/watch?v=zgvoxkGYSU4) demonstrating how to perform irrigation. They will be asked to irrigate the nose (150 ml through each nostril) daily for up to 21 days or until symptoms settle, and a SinuCleanse 19 nasal cup ('Netipot') will be provided to each subject. Patients will make their own buffered saline irrigation solution every 1 to 2 days comprising: 1 heaped teaspoon salt, one half teaspoon baking soda and 1 pint (568 ml) tap water; how to do this will also demonstrated on the video clip. We chose this particular intervention based on the provisional evidence from a previous randomised controlled trial in primary care in chronic/recurrent sinusitis (11) and from our most recent large trial also in chronic or recurrent sinusitis (13), where most patients found it acceptable and the majority continued using nasal irrigation. Participants in this group will be offered a delayed antibiotic prescription as in our previous trials(19), and advised only to use it if symptoms are getting significantly worse or not even starting to settle a little after a further week.

All study participants in both groups will have access to usual care; further medication or referral will be at the discretion of the doctor according to the normal practice of that doctor.

